## Revision History

Version number	Content of revision
Version 1	First edition
Version 2 (final edition)	Preparation of description after the case review meeting

Definitions of terms

Term	Definitions
Study period	From the day of informed consent to the final day of the follow-up observation period
Treatment period	From the first day of the treatment period to the final day of the treatment period
Day of completion of treatment period	Week 52 of the treatment period or the day of discontinuation during the treatment period
X weeks prior to the first day of the screening period	Same day of the week X weeks prior to the first day of the screening period
MT-6548 tablets	Each film-coated tablet contains 150 mg vadadustat

## 1. Introduction

This is a document that shows more detailed contents in addition to those of the study plan on the statistical analysis plan for the efficacy and safety in the fixed data of “A Phase III, Open-label Study of MT-6548 in Hemodialysis Subjects with Anemia Associated with Chronic Kidney Disease in Japan.”

## 2. Study Objectives and Design

### 2.1 Study objectives

[figure not shown]
The study evaluates the effects of MT-6548 on improvement and maintenance in hemoglobin levels and safety in patients with anemia associated with hemodialysis-dependent chronic kidney disease (HD-CKD) who are not treated with any erythropoiesis-stimulating agent (ESA).

### 2.2 Study design

Study phase: Phase III

Study type: Confirmatory study

Multicenter, uncontrolled, open-label study

Evaluation time point		Informed consent	Screening period [a]		Treatment period [b]											Final day of the follow-up observation [c]	
			First day	Visit 2	W2	W4	W6	W8	W10	W12	W16	W20	W24	Day of discontinuation			
Item	Visit	First day [b]	SV1	SV2	TV1	TV2	TV3	TV4	TV5	TV6	TV7	TV8	TV9	TV10	TV11	Final day of the follow-up observation [c]	
Permitted range (days)			-	-	-	-3	-3	-3	-3	-3	-3	-3	-3	-3	+7	or +14 [e]	
Procedure/evaluation																	
Informed consent		X															
Inclusion/exclusion criteria		X	X		X												
Patient background and history		X			X												
Height					X						X						
Dry weight, body weight [f]					X									X			
Folic acid and vitamin B 12 [g]					X										X		
Pregnancy tests [i]			X														
Hematology tests [g], [h], [i]		X	X [k]		X	X	X	X	X	X	X	X	X	X	X		
Blood biochemistry tests [g], [h], [i]		X			X	X	X	X	X	X	X	X	X	X	X		
C-reactive protein [g], [h]		X			X										X		
Iron-related measures [g], [h]		X			X	X	X	X	X	X	X	X	X	X	X		
Hepcidin [h]		X			X	X	X	X	X	X	X	X	X	X	X		
EPO [h]		X			X	X	X	X	X	X	X	X	X	X	X		
VEGF[h]		X			X										X		
Vital signs [g], [h], [m]		X			X	X	X	X	X	X	X	X	X	X	X		
Resting standard 12-lead ECG [h], [n]		X			X										X		
Fundoscopy [e]		X			X									X			
Chest X-ray [e]		X			X									X			
Duration of hemodialysis					X										X		
QOL measures (EQ-5D-5L, KDQOL)					X						X						
AE investigation					X	X	X	X	X	X	X	X	X	X	X		
Blood sampling for genetic analysis [o]																X	
Product evaluation/procedure																	
Investigation of concomitant medications/therapies					X	X	X	X	X	X	X	X	X	X	X	X	X
MT-6548 tablets [p], [q]																	
Iron supplements																	
Administered according to the dosage adjustment guidelines																	
Iron supplements administered to maintain serum ferritin values of $\geq 100$ ng/mL or TSAT of $\geq 20\%$																	

- [a] The screening period can be up to 6 weeks. Test results should be reviewed prior to transition from the first day of the screening period to screening period Visit 2 and from screening period Visit 2 to the first day of the treatment period. Re-testing can be performed as necessary.
- [b] The scheduled study visit during the treatment period shall be the dialysis day 2 days after the previous dialysis, and if it is difficult, the dialysis day 1 day after the previous dialysis.
- [c] Should not be performed if discontinued before the treatment period.
- [d] Should be performed before study drug administration (AE investigations begin after study drug administration).
- [e] Fundoscopy and chest X-ray should be performed once during the screening period. Should be performed once during Week 20 to Week 24 of the treatment period. Should be performed within 14 days after discontinuation whenever possible if discontinued during the treatment period.
- [f] Body weight should be measured before and after dialysis.
- [g] Measurements on the day of dialysis should be performed before dialysis during the screening period.
- [h] Tests during the treatment period should be performed before dialysis on the day of dialysis.
- [i] To be performed only in female subjects of childbearing potential.
- [j] Hb values should be measured in blood collected in the supine position.
- [k] Only Hb values should be measured.
- [l] Urea nitrogen levels should be measured only before and after dialysis on the first day, Week 24 of the treatment period, and on the day of treatment discontinuation.
- [m] Measurements should be made before blood sampling as much as possible. Measurements should be made in the sitting position after 5 minutes of rest.
- [n] Measurements should be made before blood sampling as much as possible. Measurements should be made in the supine position after 5 minutes of rest.
- [o] Blood should be collected once as early as possible after Week 2 of the treatment period for subjects who have given consent to the genetic analysis tests.
- [p] MT-6548 tablets should be prescribed to subjects depending on the number of their unused tablets. Subjects should be instructed to use up one bottle before opening the next.
- [q] In principle, dosage adjustments should be performed at scheduled study visits; however, an unscheduled visit may be provided for dosage adjustment if considered necessary, in cases where excessive increases or decreases in Hb values are of concern based on the Hb value time course.

## 2.3 Rationale for sample size

Twenty subjects enrolled in the treatment period

[Rationale]

The proportion of patients who are not treated with any ESA formulation is as small as approximately 10% of the total number of dialysis patients in Japan. Patients receiving any ESA formulation are allowed to register after undergoing a washout; however, the target sample size was set at 20 after consideration of the feasibility as the number of eligible patients was thought to be very limited when considering the inclusion/exclusion criteria.

## 3. Endpoints

### 3.1 Efficacy endpoints

#### 3.1.1 Primary endpoint

- (1) Mean Hb values at Week 20 and Week 24 of the treatment period
- (2) Hb value at each timepoint in the treatment period
- (3) Proportion of subjects with mean Hb values within the target range (10.0 to 12.0 g/dL), <10.0 g/dL, and  $\geq 12.0$  g/dL at each time point in the treatment period
- (4) Number of days from the first day of the treatment period required to reach the target Hb range (10.0 to <12.0 g/dL)
- (5) Hb value increase rate

#### 3.1.2 Other endpoints

- (1) Changes in mean Hb values from the first day of the treatment period at Week 20 and Week 24 of the treatment period
- (2) Proportion of subjects with a  $\geq 1.0$  g/dL increase from baseline in mean Hb values at each time point in the treatment period
- (3) Proportion of subjects receiving rescue therapy with ESA formulations, red blood cell transfusion, or phlebotomy
- (4) Study drug dosage
- (5) Total number of study drug dosage adjustments
- (6) Iron supplement dosage
- (7) Proportion of subjects receiving iron supplements via oral, intravenous, or any route.

- (8) Proportion of subjects with serum ferritin  $\geq 100$  ng/mL or TSAT  $\geq 20\%$
- (9) Changes and rate of changes in iron-related indices (serum iron, TIBC, TSAT, and serum ferritin levels) and hepcidin from the first day of the treatment period
- (10) Changes in hematocrit, red blood cell count, reticulocytes (count and rate), mean corpuscular volume, mean corpuscular hemoglobin, and erythropoietin from the first day of the treatment period
- (11) Changes and rate of changes in systolic blood pressure, diastolic blood pressure, lipids (total cholesterol, LDL-C, HDL-C, LDL-C/HDL-C ratio, triglycerides), and blood glucose from the first day of the treatment period
- (12) QOL indices (EQ-5D-5L, KDQOL)

### **3.2 Safety endpoints**

- (1) Adverse events and adverse drug reactions
- (2) Laboratory test values
  - 1) Hematology tests:

Mean corpuscular volume, mean hemoglobin, mean hemoglobin concentration, RBC distribution width, WBC count, WBC fractions (neutrophils, eosinophils, monocytes, lymphocytes, basophils), platelet count
  - 2) Blood biochemistry tests:

Total protein, albumin, blood glucose, urea nitrogen, creatinine, uric acid, CPK, total bilirubin, AST, ALT, ALP, LDH,  $\gamma$ -GTP, Na, K, Cl, Ca, P, Mg, bicarbonate, total cholesterol, LDL-C, HDL-C, triglycerides
  - 3) C-reactive protein
  - 4) Folic acid and vitamin B12
  - 5) Vascular endothelial growth factor (VEGF)
- (3) Resting standard 12-lead ECG
- (4) Dry weight
- (5) Body weight
- (6) Vital signs
- (7) Fundoscopy
- (8) Chest X-ray

- (9) Proportion of subjects with documented Hb values of  $\geq 12.0$  g/dL or  $\geq 13.0$  g/dL
- (10) Proportion of subjects with documented Hb values of  $< 9.0$  g/dL or  $< 8.0$  g/dL
- (11) Proportion of subjects with a documented Hb value increase rate of  $> 0.5$  g/dL/week
- (12) Hb value after dose reduction or interruption of the study drug
- (13) Kt/V

## 4. Definition of Derived Variables

### 4.1 Age at consent acquisition

Age (year) = Date of consent acquisition (year) – Date of birth (year)

However, when (Date of consent acquisition [month] < Date of birth [month]) or (Date of consent acquisition [month] = Date of birth [month] and Date of consent acquisition [days] < Date of birth [days]), 1 is subtracted from the traditional Japanese age system calculated above.

### 4.2 Duration of disease

The duration of disease (year) should be the period from the onset of renal anemia to the consent month and shall be the integer part + 1 digit (rounded). Duration of disease is calculated as follows:

Duration of disease (year) = (Date of consent acquisition [year] – Time of onset [year]) + (Date of consent acquisition [month] – Time of onset [month])/12

If the month of onset is unknown, the month is calculated as 1.

### 4.3 Period from the first day of hemodialysis

The period from the start of hemodialysis (year) should be the period from the start of hemodialysis (time of first hemodialysis or hemodiafiltration) to the month of consent acquisition and should be the integer part + 1 digit (rounded). The period from the start of hemodialysis should be calculated as follows:

Period from the start of hemodialysis (year) = (Date of consent acquisition [year] – Start of hemodialysis [year]) + (Date of consent acquisition [month] – Start of hemodialysis [month])/12

If the month of the start of hemodialysis is unknown, the month should be calculated as 1.

### 4.4 BMI

BMI (kg/m^2) = Dry weight (kg)/(Height [m])

Should be rounded and displayed to one decimal place.

#### **4.5 LDL-C/HDL-C ratio**

LDL-C/HDL-C ratio = LDL-C (mg/dL)/HDL-C (mg/dL)

Should be rounded and displayed to two decimal places.

#### **4.6 Number of days of drug interruptions**

The number of days of drug interruptions does not include subject's forgetting to take the drug and is defined by the following formula.

Number of days of drug interruptions (days) = Day of resumption of study drug administration – First day of study drug interruption

If there are multiple interruptions, the sum of them should be used.

Resumption day of study drug administration: Defined as “Scheduled first day of the modified dose administration” when a value of >0 mg is entered for the first time after the entry of “Changed Dose” = 0 mg in the CRF. If the drug interruption continues until Week 24 of the treatment period, days should be calculated based on the visit date after Week 24 of the treatment period as the resumption date. Specifically, if the treatment is completed or discontinued while the drug is interrupted, the day before the day of blood sampling at Week 24 for hematology tests or the day before the day of treatment discontinuation should be used.

First day of study drug interruption: Defined as “Scheduled first day of the modified dose administration” when “Changed Dose” = 0 mg is entered in the CRF.

#### **4.7 Duration of study drug administration**

For subjects who completed treatment period:

Duration of study drug administration (days) = Day of blood sampling for hematology tests at Week 24 – First day of the treatment period

For subjects who discontinued:

Study drug administration duration (days) = Day of discontinuation – First day of the treatment period

#### **4.8 Number of study drug administration days**

The number of days of study drug administration is defined by the following formula:

Number of MT-6548 administration days (days) = Period of study drug administration – Number of days of no study drug administration other than drug interruptions – Number of days of drug interruptions

## 4.9 Study drug compliance rate

Study drug compliance rate (%) = Number of days of study drug administration / (Period of study drug administration – Number of days of drug interruptions) × 100

However, if the compliance rate exceeds 100%, it should be 100%.

## 4.10 Mean daily dose

Mean daily dose of MT-6548 during each scheduled study visit period\* = Daily dose based on the physician's prescription × Period of administration (days)\*3 of the corresponding dose\*2 between the scheduled study visits\* / Period between the schedule study visits (days)\*4

\*: For each period between the scheduled study visits, the actual study visit dates will not be considered, and this variable should be fixed as follows:

- The first day of the treatment period to Week 2 of the treatment period: The first day of the treatment period (Day 1) to Day 14
- Week 2 of the treatment period to Week 4 of the treatment period: Day 15 to Day 28
- The same shall apply thereafter, and the final period between the scheduled study visits should be Week 20 to Week 24 of the treatment period: Day 141 to a blood sampling day for hematological tests at Week 24 of the treatment period.

However, for subjects who discontinued their treatment, the final period between the scheduled study visits should be up to the day before discontinuation.

\*2: If there are multiple applicable doses, the sum of the calculated values for each dose should be used.

\*3: The number of days without drug administration other than drug interruption should not be excluded from the "period of administration (days)".

\*4: 14 days up to Week 12 of the treatment period and 28 days after Week 12 of the treatment period. However, for subjects who discontinued their treatment, the final period between the scheduled study visits (days) should be the actual number of days until the day before discontinuation.

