8.4 Treatment period

From the first day of the treatment period to the day before Week 24 of the treatment period

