- [c] Not required if withdrawn prior to the treatment period.
- [d] To be performed prior to the study drug treatment (AE investigation begins after study drug administration).
- [e] Fundoscopy and chest X-ray performed once during screening period, once during Weeks 20–24 of treatment period. In the case of discontinuation of the treatment period, fundoscopy and chest X-ray should be performed within 14 days after discontinuation whenever possible.
- [f] Body weights should be measured before and after dialysis.
- [g] To be measured before dialysis on the day of dialysis during the screening period.
- [h] Tests during the treatment period should be performed before dialysis on the day of dialysis.
- [i] To be performed only in female subjects of childbearing potential.
- [j] Hb levels should be measured in blood collected in the supine position.
- [k] Only Hb levels should be measured.
- [l] Only urea nitrogen levels should be measured before and after dialysis on the first day, Week 24 of the treatment period, and on the day of treatment discontinuation.
- [m] To be measured in the sitting position after a 5-minute rest before blood sampling whenever possible.
- [n] To be measured in the supine position after a 5-minute rest before blood sampling whenever possible.
- [o] For subjects giving consent to blood sampling for genetic analysis, blood will be collected once as early as possible after Week 2 of the treatment period.
- [p] MT-6548 Tablets should be prescribed depending on the number of unused tablets by the subject. Subjects should be instructed to open a new bottle after using up the tablets in one bottle.
- [q] In principle, dosage adjustments should be performed at scheduled visits; however, an unscheduled visit may be provided for dosage adjustment, if considered necessary, in cases where excessive increases or decreases in Hb levels are of concern based on the Hb time course.

If tests and observations cannot be performed on the scheduled day, they may be performed within the permitted ranges shown below. During the treatment period, subjects are to visit the study site on the day of dialysis after a 2-day interdialytic interval; however, if this is difficult, subjects are to visit the study site on the day of dialysis after a 1-day interdialytic interval.

Table 9.1-1 Permitted ranges for study center visits

Evaluation timepoint		Reference date	Permitted range
Screening period* ¹	First day	–	–
	Visit 2	–	–

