#### 4.13 Iron supplement dosage

The dose of iron supplements is defined by the following formula.

Mean monthly dose of iron supplements during the screening period\* and each scheduled study visit period\* (tabulation period of iron supplements) = (Daily dose based on the physician's prescription × Period of administration (days) of the corresponding dose\* during the tabulation period of iron supplements)/Tabulation period of iron supplements (days)\* × 30.4375\*

- \*: The number of days of the screening period is “First day of the treatment period – First day of the screening period”.
- \*2: For each period between the scheduled study visits, the actual study visit dates are not considered, and this tabulation is fixed as follows:
  - The first day of the treatment period to Week 2 of the treatment period: The first day of the treatment period (Day 1) to Day 14
  - Week 2 of the treatment period to Week 4 of the treatment period: Day 15 to Day 28
  - The same shall apply thereafter, and the final period between the scheduled study visits should be Week 20 to Week 24 of the treatment period: Day 141 to a blood sampling day for hematological tests at Week 24 of the treatment period. However, for subjects who discontinued their treatment, the final period between the scheduled study visits should be up to the day before discontinuation.
- \*3: If there are multiple applicable doses, the sum of the calculated values for each dose should be used.
- \*4: For subjects who discontinued their treatment, the final period between the scheduled study visits (days) should be the actual number of days until the day before discontinuation.
- \*5: In this tabulation, 1 month is counted as 30.4375 days ( $365.25/12 = 30.4375$ ).

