### 7.5.2 Analysis of other endpoints

(1) Changes in mean Hb values from the first day of the treatment period at Week 20 and Week 24 of the treatment period

Descriptive statistics for change from Hb value on the first day of the treatment period to mean Hb values at Week 20 and Week 24 in the treatment period should be calculated. A paired t-test should be performed for before and after comparison of changes from the first day of the treatment period. The analysis should be conducted using the MMRM model (with compound symmetry [CS] for a variance-covariance matrix within subjects). LSMeans, its standard errors, and 2-sided 95% CI for change from Hb value on the first day of the treatment period to mean Hb values at Week 20 and Week 24 of the treatment period should be calculated.

(2) Proportion of subjects with a  $\geq 1.0$  g/dL increase in mean Hb values from the first day of the treatment period at each time point of the treatment-period.

The number, proportion, and 95% CI (Clopper-Pearson [exact] method) of the proportion of subjects with a mean Hb increase of  $\geq 1.0$  g/dL from the first day to each evaluation time point of the treatment period should be provided.

(3) Proportion of subjects who received ESA rescue therapy, blood transfusion, or phlebotomy

The number, proportion of subjects and 95% CI (Clopper-Pearson [Exact] method) of the proportion of subjects receiving rescue therapy with an ESA formulation should be provided, after the first day of the treatment period, in each period between scheduled study visits and during the entire treatment period from the first day to Week 24 of the treatment period.

The analyses same to the above subjects receiving rescue therapy with ESA formulation should be performed for subjects receiving rescue therapy with RBC transfusion or receiving phlebotomy.

(4) Study drug dosage

1) Study drug dosage

Descriptive statistics of mean daily dose should be calculated for each scheduled study visit from the first day of the treatment period up to treatment period Week 24. The time course diagram for mean daily dose should be separately prepared. 95% CI of the mean will be represented by an error bar. Each period between scheduled study visits is defined as the period between the scheduled visit and the day before the next scheduled study visit.

2) Distribution of dose of MT-6548 tablets

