### 7.5.5 Multicenter trial

For FAS, the following analysis should be conducted for each following endpoint for each site. Descriptive statistics of Hb values should be calculated at Week 24 of the treatment period (imputed by the LOCF method).

Descriptive statistics should be calculated for the mean dose of the study drug at Week 20 to Week 24 of the treatment period.

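### SAP 4.10: completers' Week 20–24 mean daily dose counts dosing up to the actual sampling day but divides by a fixed 28 days, so an off-schedule visit misstates a constant dose by up to 25%

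*SAP*

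**What the plan says.** SAP 4.10 states that the intervals between scheduled visits are fixed and that actual visit dates are ignored. With the first treatment day as Day 1, the intervals are Day 1 to 14, Day 15 to 28, and so on. The last interval departs from this rule, because it runs from "Day 141 to a blood sampling day for hematological tests at Week 24 of the treatment period".

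Note *4 of the same section sets the divisor at "14 days up to Week 12 of the treatment period and 28 days after Week 12 of the treatment period". Its only exception is for subjects who discontinue, for whom "the final period between the scheduled study visits (days) should be the actual number of days until the day before discontinuation".

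Three other places bear on the point:

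- Protocol 8.4 gives the dosing period as "From the first day of the treatment period to the day before Week 24 of the treatment period", so the last dose falls on the day before the Week 24 visit.
- SAP 7.5.2(4) defines each dose interval differently, as "the period between the scheduled visit and the day before the next scheduled study visit".
- SAP 4.13 (iron) uses the same last interval as 4.10 but has no fixed 28: its formula contains "during the tabulation period of iron supplements)/Tabulation period of iron supplements (days".

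The errata to SAP Version 2 do not change 4.10.

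**The concern.** A mean daily dose is interpretable only if the days counted above the line are the days counted below it. For discontinued subjects they are. For completers, the numerator follows the actual Week 24 date and the denominator does not, so the result depends on visit timing even when the dose never changes.

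The variable is a planned output. It is summarised as an efficacy endpoint in the "other" group (7.5.2(4)), by site in 7.5.5 as the "mean dose of the study drug at Week 20 to Week 24 of the treatment period", and across the subgroups of 7.5.6. The planned sample is 20, so site and subgroup cells can be very small and a single off-schedule subject can move a cell mean. A late visit can also produce a mean daily dose that no subject could have been prescribed.

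**Working it through.** **Inputs**

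- Start of the last interval: Day 141, with the first treatment day as Day 1 (SAP 4.10).
- Divisor for completers: 28 days (SAP 4.10, note *4).
- Week 24 window: reference Day 168, permitted Day 161–175, with the first treatment day as Day 0 (Protocol Table 9.1-1, adopted in SAP 6.2). In SAP numbering these are Day 169 and Day 162–176.
- Last dose: the day before the Week 24 visit (Protocol 8.4).
- Assumed: constant prescribed dose, no drug interruption.

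**Step 1: the plan's own 28 days.** On schedule, sampling falls on SAP Day 169 and the last dose on Day 168. Day 141 to 168 is 168 − 141 + 1 = 28 days, and 28/28 = 1.000. The plan's figure is reproduced and there is no error.

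**Step 2: off schedule.** If the visit is d days from the reference date, the numerator has 28 + d dosing days, so reported dose / true dose = (28 + d)/28. Each day adds or removes 1/28 = 3.6%.

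| Visit (protocol day) | d | Dosing days | Ratio | 300 mg reported as | 450 mg | 600 mg |
|---|---|---|---|---|---|---|
| 161 | −7 | 21 | 0.750 | 225 | 337.5 | 450 |
| 165 | −3 | 25 | 0.893 | 267.9 | 401.8 | 535.7 |
| 168 | 0 | 28 | 1.000 | 300 | 450 | 600 |
| 171 | +3 | 31 | 1.107 | 332.1 | 498.2 | 664.3 |
| 175 | +7 | 35 | 1.250 | 375 | 562.5 | 750 |

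**Step 3: which offsets are likely.** The protocol asks that "subjects are to visit the study site on the day of dialysis after a 2-day interdialytic interval", or after a 1-day interval if that is difficult. Assume a regular three-session week with the first treatment day on the session after the 2-day interval. The sessions inside the window then lie at d = −7, −5, −3, 0, +2, +4 and +7, with ratios 0.750, 0.821, 0.893, 1.000, 1.071, 1.143 and 1.250. If the first treatment day falls on another session, the offsets change but the formula does not.

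**Step 4: when the result exceeds 600 mg.** The average prescribed dose must exceed 600 × 28/(28 + d): 560 mg at d = +2, 525 mg at +4, 480 mg at +7.

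**Step 5: effect on a group mean.** One subject on 300 mg seen at +7 is overstated by 300 × 7/28 = 75 mg, which moves a mean of n subjects by 75/n: 75 mg for n = 1, 18.8 mg for n = 4, 3.75 mg for n = 20. Cell sizes are not given, so n is an assumption apart from the planned total of 20.

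**Step 6: other day counts.** If the sampling day is counted as a dosing day, the ratios are 22/28, 29/28 and 36/28 (78.6%, 103.6%, 128.6%), so even an on-time visit is overstated by 3.6%. If the day numbers of Table 9.1-1 are used without conversion and the sampling day is excluded, they are 20/28, 27/28 and 34/28 (71.4%, 96.4%, 121.4%). The range is 50 percentage points wide in every case.

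**The case against.** The best reply is that the intended rule is clear and harmless. SAP 4.10 opens with a fixed grid, note *4 gives a fixed 28 days, and 7.5.2(4), read on nominal dates, gives Day 141 to 168. On that reading the sampling-day end point is a stray phrase in a translated document, and a programmer following the grid would compute 28/28. That is a plausible account of how the text arose, but it does not settle what to do. The sampling-day clause is specific to the last interval and would have no meaning if the grid prevailed, and 7.5.2(4) does not say that it overrides 4.10. Nor does a fixed Day 141–168 grid fully work: it corrects late visits, but a completer seen 7 days early still has only 21 dosing days over 28.

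Several narrower objections stand:

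- 75% and 125% are window extremes. A visit near the reference date gives a small error, and the preferred session may well fall exactly on it.
- The iron formula is only partial support. Section 4.13 also says that actual visit dates are ignored and spells out actual days only for discontinued subjects. It lacks the fixed 28 but is not a fully specified counterpart.
- No stated figure is miscalculated. This is an inconsistency between two definitions, and it affects one descriptive variable in one interval.

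**Conclusion.** The concern holds, at minor severity. Followed as written, SAP 4.10 reports a completer's constant Week 20–24 dose at (28 + d)/28 of its true value: exact on schedule, 75% at the earliest permitted visit and 125% at the latest. This takes the last dose as the day before sampling and the window from Table 9.1-1; other day counts move the ends by about 3.6 points without removing the error. The frequency is unknown because the documents give no actual visit dates. Earlier intervals, whose numerator and denominator are both fixed, are unaffected, and so are the cumulative dose (4.11) and all Hb and adverse-event analyses.

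**What to change.** In SAP 4.10, end the completer's last interval on the day before the Week 24 sampling day, and in note *4 set the denominator for completers to the actual number of days from Day 141 to that same day. This extends to completers the rule already used for discontinued subjects, and the ratio becomes 21/21, 28/28 or 35/35 = 1 wherever the visit falls in the window. State that the last interval is an exception to the rule of ignoring actual visit dates, and give 7.5.2(4) the same end point for that interval (nominally Day 168).

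The cost is a short SAP edit (the first note and note *4 of 4.10, and 7.5.2(4)) and about one line of code. No data collection or trial procedure changes.
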